- **Pulse oximeter probe** (MasimoSET, Irvine, CA, USA) is cleared (K061204). It will be used to measure oxygen saturations and heart rate.
- **MP100 Biopac data acquisition** (Biopac Systems Inc., Goleta, CA, USA) will be used to collect data from the monitoring devices.

Study Population:

Up to thirty subjects at Arkansas Children's Hospital (ACH) will be consented to retain twenty-four participants in the study. Inclusion criteria will include:

- Chronological age greater than 28 days
- Gestational age at birth less than 33 weeks as documented in the subjects' initial history and physical

Title: Effect of Synchronized vs. Continuous High Flow Nasal Cannula using Neurally Adjusted Ventilatory Assist on Work of Breathing in Infants with Bronchopulmonary Dysplasia
PI: [name]

- A diagnosis of BPD, defined for this study as having received supplemental oxygen for greater than or equal to 28 days from birth
- Currently receiving NIV in the form of nCPAP, NIV NAVA, NIPPV, or HFNC

Exclusion criteria will include:

- Post-menstrual age (gestational age plus chronological age) of greater than 50 weeks 0 days
- Oxygen requirement greater than 40% at the time of enrollment
- Transcutaneous CO₂ measurements > 80
- Currently receiving invasive ventilation
- Major congenital anomalies of the heart and/or lungs
- Bilateral phrenic nerve palsy
- Major gastrointestinal malformations, including gastroschisis, omphalocele, and congenital diaphragmatic hernia
- Currently receiving treatment for pneumonia or suspected/confirmed sepsis

Study Design/Procedures:

Parental consent will be obtained prior to study. Synchronized HFNC is not an option on current HFNC devices, which provide only a constant flow of gas. NAVA devices only provide pressure measurements during NAVA in intubated patients, or NAVA using non-invasive nasal prongs (NIV NAVA). Nonetheless, many neonatal intensive care units (NICUs), including the ACH NICU, use nasal cannulas designed for low or high flow, but not approved for nasal CPAP, to attempt provision of nasal CPAP and NIV NAVA. For our study, we will use the cannula currently in use at ACH (RAM cannula, Neotech, Valencia, CA, USA) and as currently FDA approved, and set the NAVA ventilator so that it responds similarly to a HFNC. The RAM cannula will be used to provide both continuous and NAVA-synchronized HFNC.

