The provision of continuous HFNC with displayed flow rates and Edi signal will be done using the Servo ventilator and the recently developed HFNC software for this ventilator. To more accurately record flow rates, a pneumotachograph (unheated, calibrated, 0-10 liters per minute (LPM), Hans-Rudolph, Shawnee, KS, USA) will be inserted into the inspiratory limb of the ventilator circuit and flows will be recorded on the data acquisition system. The pneumotachograph will also be used to translate pressure settings into flow settings for the synchronized HFNC portion of the study.

During NAVA-synchronized HFNC, the NIV NAVA mode will be set in such a way that synchronized HFNC will be provided. A minimal end-expiratory flow of 2 LPM will be provided using the positive end expiratory pressure (PEEP) setting in the NIV NAVA

Title: Effect of Synchronized vs. Continuous High Flow Nasal Cannula using Neurally Adjusted Ventilatory Assist on Work of Breathing in Infants with Bronchopulmonary Dysplasia
PI: [name]

mode on the ventilator. The PEEP setting corresponding to 2 LPM via the pneumotachograph will be used. In order to deliver the desired peak flow rate with each neurally-triggered breath, a NAVA level of 15 cmH₂O/µV will be set, then the maximum pressure setting that corresponds to the desired flow rate using the pneumotachograph will be used for the study. The subject will thus be provided with "synchronized HFNC".

This contrasts with the constant-flow trials when subjects will receive a constant and non-synchronized flow using the HFNC software on the ventilator.

WOB for this study will be calculated by a computerized program utilizing a process which has been used in a previously published study.²⁸ Edi signal analysis will also be performed by a specifically developed computer program.

Prior to the study period each subject will have the following monitoring equipment placed (if not already present): Edi catheter, transcutaneous monitor (TCM4, Radiometer, Brea, CA, USA) to measure CO₂ and O₂ levels, pulse oximeter probe (MasimoSET, Irvine, CA, USA) to measure oxygen saturations and heart rate, and RIP bands (SleepSense, MFI Medical, San Diego, CA, USA) around the chest and abdomen to measure breathing movements and relative tidal volume.

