Each subject will be randomized on the day the study is to occur to begin with either NAVA-synchronized or continuous HFNC before crossing over to the other mode to serve as his/her own control. The same RAM cannula will be used in both study arms and will provide a leak of 60-80% as recommended by the product manual. The delivery of high flow during both synchronized and continuous HFNC will be given at two commonly provided levels of high flow: 6 LPM and 8 LPM, given in the same order in each mode (6 LPM then 8 LPM). Each subject will receive 15-minute trials of each mode-level combination, for a total of four trials performed in succession. During each trial, the first 10 minutes will be used for stabilization, and the last 5 minutes will be used for data collection, as has been done in previous trials.^{20, 27-28} There will be approximately one to two minutes between each trial to adjust ventilator settings. Thus, the mode-level combinations of the trials will be as follows: for subjects randomized to begin with synchronized support: synchronized-6 LPM, synchronized-8 LPM, unsynchronized-6 LPM, unsynchronized-8 LPM. For subjects randomized to begin with unsynchronized support: unsynchronized-6 LPM, unsynchronized-8 LPM, synchronized-6 LPM, synchronized-8 LPM.

Title: Effect of Synchronized vs. Continuous High Flow Nasal Cannula using Neurally Adjusted Ventilatory Assist on Work of Breathing in Infants with Bronchopulmonary Dysplasia
 PI: [name]

[figure not shown]

Figure 1. Flowchart depicting order of trials based on initial randomization.

The flows described in the NAVA-synchronized trials refer to the peak flow provided during inspiration. A baseline flow rate of 2 LPM will be provided expiration in these trials (using the PEEP setting corresponding to the appropriate flow rate). During the unsynchronized trials, the continuous high flow rate will be provided (as is common practice with the use of HFNC). During the NAVA-synchronized HFNC trials, the Edi trigger will be set to 0.5 microvolts, apnea time to 5 seconds, back up rate to 10 breaths per minute, and backup pressure settings will be set to provide an estimated peak flow of 6 or 8 LPM according to the designated trial (again, using the pressure setting corresponding to the appropriate flow rate).

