Servo-u ventilators and Servo Tracker Software (Maquet Critical Care, Solna, Sweden) will be used in order to track Edi signal. The MP100 Biopac data acquisition (Biopac Systems Inc., Goleta, CA, USA) will be used to collect data from the monitoring devices. HFNC will be delivered using appropriately sized RAM cannula to allow for air leak around the subject's nares. Persistent (>20 seconds) bradycardia (less than 100 beats per minutes), desaturation (<85%), or hypercarbia (transcutaneous CO₂ >70) will result in cessation of the study.

Title: Effect of Synchronized vs. Continuous High Flow Nasal Cannula using Neurally Adjusted Ventilatory

Assist on Work of Breathing in Infants with Bronchopulmonary Dysplasia

PI: [name]

Risks and Benefits:

Infants often have gagging and may have vomiting when a gastric tube, such as the NAVA catheter, is removed or replaced. Rarely, patients could have a gastric tube go into a place besides the stomach or coil in the esophagus. We should be able to detect if this occurs using the placement screen on the ventilator because the NAVA catheter has electrodes on it that detect the electrical activity of the heart and diaphragm, which can be used to determine the location. In extremely low birth weight infants, transcutaneous monitors (TCOMs) can cause skin burning. These effects are not seen in larger infants like those included in this study. There is a small risk of loss of confidentiality inherent in all research. We will do everything possible to protect the subjects' confidentiality.

There may or may not be direct medical benefit to the subjects involved in this study. The subjects will have continuous carbon dioxide and oxygen monitoring during the study and if any subject has any problems we will be able to detect and respond to this quickly. If a subject shows apparent improvement while using particular HFNC settings, we may be able to suggest to the treatment team that these settings be continued or the current settings adjusted accordingly. If a subject was already performing well on NIV, there may or may not be an improvement during the study. Subjects performing well on NIV will still undergo the trials of settings and interfaces if enrolled in this study. If using synchronized HFNC improves WOB in the subjects included in this study, then we hope the information learned from this study will benefit other infants with BPD needing respiratory support in the future.

Data Handling and Recordkeeping:

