We plan to recruit twenty-four neonates being treated for BPD with NIV. Based on the previous study conducted by Lee et al, using swing Edi to estimate WOB with NIPPV vs NIV NAVA, a 20% reduction in the primary outcome is expected.²⁰ A sample size of twenty-four subjects achieves 81% power to detect a 20% change in the primary outcome. This sample size is based on a two-sided alpha of 0.05. Randomized subjects that do not complete the study will be replaced and will not be included in data analysis. Potential reasons for withdrawal from the study include:

- Serious adverse effects believed to be related to the investigational device
- Intolerable side effects of the study procedures
- Investigator believes it is in the best interest of the subject to discontinue study participation
- Parents request withdrawal from the study

Adverse Event:

An adverse event (AE) is any medical occurrence that develops or worsens in severity during the course of the study, whether or not it has a causal relationship to the study treatment. Concurrent illnesses or injuries should be regarded as AEs. Abnormal results of diagnostic procedures, including abnormal laboratory values, are considered AEs if the abnormality:

Title: Effect of Synchronized vs. Continuous High Flow Nasal Cannula using Neurally Adjusted Ventilatory

Assist on Work of Breathing in Infants with Bronchopulmonary Dysplasia

PI: [name]

- results in study withdrawal
- is associated with a serious adverse event
- is associated with clinical signs or symptoms
- leads to additional treatment or to further diagnostic tests
- is considered by the investigator to be of clinical significance

Serious Adverse Event (SAEs):

An adverse event is “serious” if it involves considerable detriment or harm to one or more persons (who may or may not be subjects), or requires intervention to prevent one or more persons from experiencing considerable detriment or harm. SAEs include

- death
- life-threatening
- requires or prolongs hospital stay
- results in persistent or significant disability or incapacity
- a congenital anomaly or birth defect

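### Infants may enter with a transcutaneous CO₂ of up to 80, but the session must stop if the value stays above 70, with no exception for those who start there

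*Combined protocol and SAP*

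**What the plan says.** All references are to the combined protocol and SAP.

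- **Entry limit (Study Population, exclusion criteria).** The carbon dioxide criterion reads, in full, "Transcutaneous CO₂ measurements > 80". It gives no unit and no time of measurement. The oxygen criterion beside it does give a time: "Oxygen requirement greater than 40% at the time of enrollment".
- **Safety stop (Study Design/Procedures).** "Persistent (>20 seconds) bradycardia (less than 100 beats per minutes), desaturation (<85%), or hypercarbia (transcutaneous CO₂ >70) will result in cessation of the study". The limit is an absolute level. Nothing refers to the infant's starting value.
- **Order of events (Study Design/Procedures).** "Prior to the study period each subject will have the following monitoring equipment placed (if not already present"), and the list that follows includes the Edi catheter and the transcutaneous monitor. "Each subject will be randomized on the day the study is to occur". In each 15-minute trial, "the first 10 minutes will be used for stabilization, and the last 5 minutes will be used for data collection". Each infant has four trials.
- **Stopped infants (Sample size and power calculation).** "Randomized subjects that do not complete the study will be replaced and will not be included in data analysis".
- **Spare places (Study Population).** Up to thirty infants "will be consented to retain twenty-four participants in the study".

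**The concern.** The two limits apply to the same measurement and leave a band, above 70 and up to 80, in which an infant qualifies for the study and also meets the condition for ending it. I found nothing elsewhere in the document that reconciles them: no baseline exception, no change-from-baseline definition, no eligibility check on the study day and no instruction for an infant who starts in the band.

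If the rules are followed as written, an infant who stays in the band is consented, instrumented and randomized, then stopped before any data are taken. Risks and Benefits lists gagging, vomiting and misplacement as hazards of the catheter, so the burden is real where the catheter is not already in place. If staff instead let the session run, they set aside a mandatory safety rule, which is a departure from the protocol's procedures.

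Stated eligibility is also wider than the group that can ever be analysed, so a reader of the results would be misled about whom they describe.

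A smaller consequence falls on safety recording. Under Adverse Event, an abnormal diagnostic result counts as an event if it leads to withdrawal. Under Monitoring, Recording and Reporting of AEs, a condition already present at screening does not. An infant stopped at an unchanged value of, say, 75 could fall under both.

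**Working it through.** **The two rules side by side**

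| Transcutaneous CO₂ (steady) | Excluded at entry (> 80)? | Meets stop (> 70 for > 20 s)? |
|---|---|---|
| 70 or below | No | No |
| Above 70, up to and including 80 | No | **Yes** |
| Above 80 | Yes | Not applicable |

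The middle row is the conflict. It bites only if the value is still above 70 on the study day. An infant who falls to 70 or below on study support is unaffected.

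**Timing for an affected infant**, assuming the value is above 70 from the start of the first trial:

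1. Earliest stop: just over 20 s.
2. First data window opens at 10 min × 60 = 600 s.
3. Gap: 600 − 20 = 580 s = 9 min 40 s.
4. Windows collected: 0 of 4, which is 0 of 4 × 5 = 20 planned minutes. The result is the same whichever mode comes first.

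**Cost in places.** Spare places are 30 − 24 = 6, and each affected infant uses one.

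**Effect on completion.** The document gives no share of infants in the band, so this is illustration only and the conclusion does not rest on it. Suppose a share f of those consented is stopped for this reason, independently, and nobody is lost for any other reason. The chance of reaching 24 completers is P(X ≥ 24) with X ~ Binomial(30, 1 − f):

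| Assumed f | P(at least 24 complete) |
|---|---|
| 10% | 97% |
| 15% | 85% |
| 20% | 61% |
| 25% | 35% |
| 30% | 16% |

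**Power.** The stated 81% is not in dispute here. It cannot be reproduced because the standard deviation of the paired differences is not given. Working backwards, a two-sided paired t-test at 0.05 with n = 24 and 81% power needs a standardized effect of about 0.605. For a 20% change, that implies a standard deviation of about 0.20 / 0.605 = 33% of the mean. Since stopped infants are replaced, the analysed number stays at 24 as long as the spare places last, and this figure does not move.

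**The case against.** The strongest reply is that the limits govern different moments and different support. Entry is judged on whatever non-invasive support the infant is receiving, whereas the stop applies on study high flow at 6 or 8 LPM. The Background notes that high flow clears carbon dioxide from the nasopharyngeal dead space, so an entry value of 71–80 need not persist. That is correct, and it makes the conflict conditional. It does not remove it. Infants enter already on non-invasive support, the Background cites studies finding high flow similar in efficacy to other forms, and nothing in the document supports expecting a fall below 70 before the 20-second limit runs out.

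A second reply is that the monitor is on before the trials begin, so staff would see a high value and could withdraw the infant in the infant's best interest, a reason the protocol allows. That route exists. It still costs a consented place and any catheter placement, and it leaves to discretion what an eligibility rule should settle. The document neither ties that pre-trial reading to eligibility nor says whether it precedes randomization.

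Third, no harm to the primary result has been shown. This stands: the frequency is unknown, neither mode is favoured, and the sample size is unchanged. Two details also carry little weight. The missing unit creates little practical ambiguity, since one transcutaneous monitor is named. And any absolute stop at 70 keeps persistently higher infants out of the analysis, so the fault lies in admitting them, not in the stop itself.

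Finally, reading hypercarbia as newly arising hypercarbia would resolve the matter, but the text defines it only by the level.

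**Conclusion.** The concern holds. Infants above 70 and up to 80 are eligible under one rule and must be stopped under another if they remain there, and nothing in the document reconciles the two. Each affected infant yields 0 of 4 data windows and uses 1 of 6 spare places. How many would be affected cannot be determined from the document.

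This rests on three readings: that ending the study means ending that infant's session; that the stop is mandatory, as its wording indicates; and that the infant's value is still above 70 on the study day.

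The matter is one of participant protection, feasibility and a clear description of the population. It is not a bias in the synchronized-versus-continuous comparison. It should be fixed, because as written the protocol admits infants whom its own safety rule may bar from contributing data.

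**What to change.** Change the exclusion to transcutaneous CO₂ above 70, or somewhat lower to leave room before the stop. Specify that it is read on the study day before randomization, in the same stated unit as the stopping rule. Where possible, take the reading before any catheter is placed solely for the study.

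This is a one-line amendment. Its cost is a somewhat smaller eligible pool, by a share the document does not give, including some infants who might have fallen to 70 or below and completed.

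If the clinical team wants infants at 71–80, keep the entry limit and redefine the stop for them, for example as a stated rise from the study-day baseline or a limit above 80. That loosens a protection, so it is a clinical judgement that the medical monitor and the IRB would have to accept. Either route closes the gap, and neither alters the sample size or the analysis.

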The Principal Investigator will carefully monitor study procedures to protect the safety of research subjects, the quality of the data and the integrity of the study. Each subject will be assigned a unique identifying code or number. The key to the code will be kept in a locked file in a research office. Only the principal investigator and sub-investigators will have access to the code and information that identifies the subject in the study. Demographic and clinical information, such as gestational age, date of birth, gender, race/ethnicity, pregnancy complications, and clinical diagnoses, will be obtained from the medical record and kept on a password protected computer. All data will be de-identified after analysis is complete by destroying the code key. De-identified data will be maintained as per UAMS and ACRI policy (currently all data will be kept until the last subject is 21 years of age plus 2 years) and destroyed per institutional guidelines.

Title: Effect of Synchronized vs. Continuous High Flow Nasal Cannula using Neurally Adjusted Ventilatory Assist on Work of Breathing in Infants with Bronchopulmonary Dysplasia
PI: [name]

Data Analysis:

The primary hypothesis is that WOB estimated by swing Edi will be less during synchronized HFNC compared to continuous HFNC. Statistical analysis will be performed in conjunction with the Arkansas Children's Research Institute (ACRI)/University of Arkansas for Medical Sciences (UAMS) Department of Pediatrics Biostatistics program. A randomization list of synchronized vs. continuous HFNC will be provided by the biostatistics team.

Data collected will be checked for outliers and extreme values, as well as distributional assumptions of the parametric statistical tests. Paired sample t-test will be used to compare the primary and secondary outcomes, as well as safety data, under the two NIV methods when such assumptions are met. When necessary, multivariate analysis that may be more powerful in the presence of high correlation between the outcomes will be conducted for both primary and secondary outcomes. When significant deviation from assumptions is encountered, nonparametric alternatives such as Wilcoxon signed-rank test will be used. Statistical analyses will be performed using SAS (Version 9.4, SAS Institute, Cary, NC, USA) statistical software.

Sample size and power calculation:

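### The planned paired tests ignore the randomised mode order, so drift over the session would cost power and, if the sequences end unequal, shift the mode estimate

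*Combined protocol and SAP*

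**What the plan says.** Under Study Design/Procedures the order of the modes is randomised: "Each subject will be randomized on the day the study is to occur to begin with either NAVA-synchronized or continuous HFNC before crossing over". The session is continuous: "Each subject will receive 15-minute trials of each mode-level combination, for a total of four trials performed in succession". Both flow levels of one mode are completed before either level of the other, with one to two minutes between trials. Within each trial, "During each trial, the first 10 minutes will be used for stabilization".

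The Data Analysis section states "Paired sample t-test will be used to compare the primary and secondary outcomes" and, if assumptions fail, "nonparametric alternatives such as Wilcoxon signed-rank test will be used". Neither test has a period or sequence term. The multivariate option in the same paragraph is aimed at correlation between outcomes, not at order. On allocation there is one sentence: "A randomization list of synchronized vs. continuous HFNC will be provided by the biostatistics team". Blocking and allocation ratio are not stated.

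On losses, Sample size and power calculation says: "Randomized subjects that do not complete the study will be replaced and will not be included in data analysis". It does not say which sequence a replacement receives. Study Population adds that up to thirty infants "will be consented to retain twenty-four participants in the study".

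**The concern.** Within any one infant, mode and half of the session are completely confounded. Only the comparison between the two sequences separates them, and the planned tests discard the sequence.

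Swing Edi could change over an hour for reasons unrelated to mode. The stabilisation minutes deal with settling after a switch, not with a trend across the session. Such a trend adds to the synchronized-minus-continuous difference in one sequence and subtracts from it in the other. With equal sequences it cancels in the mean but inflates the SD, so the test becomes conservative and loses power. With unequal sequences, a fraction of it is reported as an effect of mode.

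Equal sequences are not assured. The list may or may not be blocked, and even a blocked list can end unequal if non-completers are dropped and replaced from the next entry.

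**Working it through.** **Inputs from the documents.** n = 24, a 20% reduction in swing Edi, two-sided alpha 0.05 and 81% power (Sample size and power calculation). Four 15-minute trials with three gaps of 1–2 minutes (Study Design/Procedures) give 4×15 + 3×(1 to 2) = 63–66 minutes.

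**Assumptions.** The documents give no SD of the within-infant difference and no drift size. Drift is varied from 0 to 20% of mean swing Edi. The plan does not say how the 6 and 8 LPM trials enter the test, so one difference per infant is used. The same argument applies at each flow separately, because the two modes are still half a session apart.

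**The plan's own figure.** The 81% cannot be reproduced without an SD; it can only be back-solved. From the noncentral t on 23 df, 81% power for a 20-point difference needs an SD of differences of 33.06% of the mean (standardised effect 20/33.06 = 0.605).

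**Algebra.** Let D be synchronized minus continuous, τ the mode effect and π the drift (second half minus first). Then E(D) = τ − π when synchronized comes first and τ + π when continuous comes first.

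- Bias of the paired mean = π × (n continuous-first − n synchronized-first)/24.
- At 12:12 the bias is zero and the expected sample variance is 33.06² + π² × 24/23. For π = 10 the SD becomes √(1093.1 + 104.3) = 34.6; for π = 20 it becomes √(1093.1 + 417.4) = 38.9.

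**Results at 12:12** (200,000 simulations per cell):

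| Drift | Paired-t power | Paired-t type I error |
|---|---|---|
| 0% | 81% | 5.0% |
| 5% | 80% | 4.8% |
| 10% | 78% | 4.1% |
| 15% | 75% | 3.2% |
| 20% | 70% | 2.2% |

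The period-adjusted t-test (22 df) stays at about 81% power and 5% type I error throughout.

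**Results at unequal splits.**

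- 15:9: the bias is π × 6/24, that is 1.25, 2.5 and 5 points at 5, 10 and 20% drift. Paired-t type I error is 5.1, 5.4 and 6.2%. At 10% drift its power is 67% or 87%, depending on the direction of drift; the adjusted test has 78% either way.
- 16:8: the bias is π × 8/24, that is 1.7, 3.3 and 6.7 points. Type I error is 5.4, 6.5 and 9.6%. The adjusted test has 76% power.
- 14:10: type I error does not exceed 5% over this range of drift.

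**How likely is an unequal split?** Under simple 1:1 randomisation of 24, exactly 12:12 has probability 16%, 15:9 or worse 31%, and 16:8 or worse 15%. With a balanced 15:15 list and 6 of 30 lost at random (hypergeometric), 14:10 or worse has probability 17% and 15:9 has 1.7%.

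**Averaged over simple randomisation.** The paired t-test is unbiased with type I error 5.0%. Its power is about 80, 77 and 68% at 5, 10 and 20% drift.

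**The case against.** The strongest reply is that randomising the order is itself the protection against drift. Averaged over the randomisation, the planned test is unbiased and holds its 5% level. That is correct, and the bias above is conditional on the split the trial happens to get. The loss of power remains, even at exact balance.

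Second, the drift is wholly assumed, and 20% equals the entire expected mode effect. At 5% drift and 12:12 the loss is about one point. If the planning SD came from paired differences in the cited randomised crossover trial, it may already contain order variation, and the power loss is then overstated. Both points stand.

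Third, imbalance may be rarer than the 6-of-30 figure suggests. Infants are randomised on the study day, so those lost between consent and that day need not use a list entry. With a balanced list, a 14:10 split needs more than two losses after randomisation and 15:9 more than four. The 17% and 1.7% are therefore an upper case, and silence on blocking is not evidence of simple randomisation.

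Fourth, period adjustment is not free. Averaged over simple randomisation it has 79.1% power, against about 81% for the paired t with no drift and 80% at 5% drift. That is a reason to block the list, not to ignore the sequence: at 12:12 the cost is about 0.2 points.

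**Conclusion.** The concern holds. The design randomises order, the analysis makes no use of it, and nothing elsewhere in the document makes up for that. Near balance the planned test is valid but conservative, with power falling from 81% to 78% at 10% drift and 70% at 20%. Type I error rises only at splits of 15:9 or worse, reaching 9.6% at 16:8 with 20% drift.

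These sizes rest on the back-solved SD of 33%, on an assumed drift common to all infants, and on one difference per infant. With small drift and a blocked list the effect is minor. The change should still be made, because the sequence is already recorded and using it costs almost nothing when the split is balanced.

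**What to change.** 1. **Primary analysis.** Pre-specify the period-adjusted crossover t-test: compare the within-infant first-half-minus-second-half differences between the two sequences (22 df). Half the difference between the sequence means estimates the mode effect.
2. **Fallback.** Replace the signed-rank test with the rank-sum test on the same differences. At 12:12 with no drift this costs about 2 points of power (about 77% against 78–79%). At 20% drift it keeps about 77%, where the signed-rank test falls to 67–68%.
3. **If a mixed model on all four trials is preferred.** Include mode, flow, period and sequence, plus an infant-by-mode random term. With a random intercept alone, simulated type I error was 8.2, 11.3 and 15.6% when infant-by-mode variation made up 30, 50 and 70% of the variance of the differences.
4. **Allocation.** State that the list is 1:1 in blocks, and have the biostatistics team give each replacement the vacated sequence, so that the final split stays at or near 12:12.

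The cost is SAP wording and list generation, with no new data or infants. One degree of freedom costs about 0.2 points of power at 12:12. With no drift the cost would be about 3 points at 15:9 (78%) and 5 at 16:8 (76%), most of which item 4 avoids. A period term does not remove carryover from one mode to the next, and the SAP should say so.

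### The safety comparison has no defined variables and does not use the protocol's own heart rate, saturation and CO₂ thresholds, so neither short nor long episodes need show in it

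*Combined protocol and SAP*

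**What the plan says.** The only planned comparison of safety between modes is one sentence in Data Analysis: "Paired sample t-test will be used to compare the primary and secondary outcomes, as well as safety data, under the two NIV methods". This applies when distributional assumptions hold; otherwise "nonparametric alternatives such as Wilcoxon signed-rank test will be used". The section does not say which variables are safety data, how a continuous signal becomes one value per infant and mode, or how paired yes/no data would be handled.

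Study Design/Procedures sets physiological limits: "Persistent (>20 seconds) bradycardia (less than 100 beats per minutes), desaturation (<85%), or hypercarbia (transcutaneous CO₂ >70) will result in cessation of the study". The signals are available. The monitoring list includes a "pulse oximeter probe (MasimoSET, Irvine, CA, USA) to measure oxygen saturations and heart rate" and a transcutaneous monitor, and monitor data go to the acquisition system. Each mode is given in two 15-minute trials, in which "the first 10 minutes will be used for stabilization, and the last 5 minutes will be used for data collection".

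Under Specific Aims, saturation and transcutaneous CO₂ are secondary outcomes. Heart rate is not a listed outcome.

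The section on sample size and power adds: "Randomized subjects that do not complete the study will be replaced and will not be included in data analysis". Adverse events are logged from consent to last device use, but no tabulation by mode is described.

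**The concern.** The stopping limits define harm by a threshold and a duration, but no between-mode analysis is on that scale. Two kinds of episode can therefore go unseen in the safety comparison.

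- **20 seconds or less.** These do not trigger the stop rule. If the safety variable is a 5-minute average they barely move it, and outside the collection window they do not count at all.
- **More than 20 seconds.** These end the study for that infant, who then does not complete, is replaced and is left out of the analysis. This is selection on the safety outcome itself.

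The protocol describes synchronized HFNC as novel and not yet studied in neonates with BPD, and flow falls to 2 LPM in expiration. A non-significant paired test on averages in completers could be read as evidence that the two modes are equally well tolerated, when the analysis had little chance of showing otherwise.

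**Working it through.** **The plan's own figure.** "A sample size of twenty-four subjects achieves 81% power to detect a 20% change in the primary outcome". No SD is given, so the 81% can only be solved backwards. For a paired t-test with n = 24 and two-sided alpha 0.05, it implies a standardized difference of 0.605, that is, an SD of differences of 20% / 0.605 = 33% of the mean. The figure concerns swing Edi only; no power is stated for safety.

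**Inputs from the documents.** Window 5 min = 300 s per trial; 24 analysed; up to 30 consented; limits of 85%, 100 and 70 with a 20-second persistence rule.

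**Assumed inputs (the documents give none).** Depth, duration and frequency of episodes, and an SD of paired differences in mean saturation of 1, 2 or 3 points.

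**Step 1: dilution by averaging.** Shift in mean = depth × duration / 300.
- Saturation 95% to 80% for 19 s: 15 × 19 / 300 = 0.95 points.
- Heart rate 150 to 90 for 19 s: 60 × 19 / 300 = 3.8 beats.
- Falls of 10 to 15 points: 0.17 to 0.25 points for 5 s, 0.33 to 0.50 for 10 s.
- If both windows of a mode are averaged: 0.95 / 2 = 0.475 points.

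**Step 2: power of the paired test on averages.** Six of 24 infants have one 19-second, 15-point fall in one mode and none in the other. Average difference = 6 × 0.95 / 24 = 0.24 points. Simulated power:

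| Analysis | SD 1 | SD 2 | SD 3 |
|---|---|---|---|
| Paired t, one window per mode | 16% | 8% | 6% |
| Paired t, two windows averaged | 8% | 6% | 5% |

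A signed-rank test on the same one-window averages does no better (about 15% at SD 1 and 6% at SD 3).

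**Step 3: the same question on an any-episode scale.** Six versus 0 discordant infants gives an exact McNemar p of 2 × 0.5⁶ = 0.031. That is the smallest one-sided split reaching 0.05, since 5 versus 0 gives 2 × 0.5⁵ = 0.0625. The fair comparison with Step 2 is power, taking episodes as independent between modes:

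| Infants with an episode, one mode vs the other | Exact McNemar power, n = 24 |
|---|---|
| 25% vs 0% | 58% |
| 25% vs 5% | 30% |
| 50% vs 5% | 93% |
| 15% vs 5% | 5% |

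**Step 4: episodes beyond 20 seconds.** "Up to thirty subjects at Arkansas Children's Hospital (ACH) will be consented to retain twenty-four participants in the study" leaves room for 30 − 24 = 6 infants. As an extreme case, suppose all six were randomized and stopped on the thresholds. The stop rate would be 6/30 = 20% (95% CI 8% to 39%). The analysed set would show 0/24, with a one-sided 95% upper limit of 1 − 0.05^(1/24) = 12%.

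**Step 5: share of exposure observed.** The windows cover 5/15, one third, of each trial. On the stated collection scheme, an episode in the stabilization period is outside the data.

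**The case against.** Four points on the other side carry weight.

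- **Averages are not specified.** A reader might infer that the plan commits to a t-test on mean levels. It does not: safety data are undefined, and a signed-rank test on seconds below a threshold would already fit the wording. What stands is that the variable is undefined and averages are not excluded.
- **The named limits are not brief crossings.** A reader might infer that the harms the protocol names are averaged away. The text names episodes persisting beyond 20 seconds, and those stop the study. Averaging affects only shorter episodes; the named ones are lost by exclusion and replacement.
- **Events are not simply lost.** All adverse events are logged, infants are monitored continuously and a medical monitor reviews serious events. It is therefore too strong to say that a real difference would be reported as none. Frequent dips could also be detected: if half the infants had 12-point dips totalling 60 s in one mode (a shift of 2.4 points), the t-test would have 95%, 67% or 42% power at SDs of 1, 2 or 3. None of this supplies a comparison by mode, however, and a brief dip need not meet the protocol's conditions for recording an abnormal result as an adverse event.
- **Event-based tests are weak here too.** At 15% versus 5%, exact McNemar power is about 5%. This stands, and it argues for estimates ahead of tests.

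Comparing safety is also not a listed aim, and exposure is only four 15-minute trials.

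**Conclusion.** The point holds in a limited form. The plan tests undefined safety data with a paired t-test or signed-rank test, and no comparison between modes uses the protocol's own thresholds. Episodes of 20 seconds or less would be heavily diluted if 5-minute averages are used. Longer ones remove the infant from the analysis. So neither kind need show in the safety comparison, although the adverse event log remains.

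The dilution arithmetic is exact given depth and duration. The power figures rest on assumed SDs and episode rates. The loss of longer episodes follows from reading the cessation rule together with the replacement rule, and its size is unknown. This is a cheap improvement and does not affect the primary analysis.

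**What to change.** In Data Analysis, replace the reference to safety data with defined variables per infant and mode: any crossing of each threshold, seconds beyond each threshold, and study stops. Compute them from the recorded signals over the full 15 minutes of each trial.

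- **Population.** Report by mode received for every randomized infant exposed, including those stopped and replaced. In completers alone, the length of any one episode is truncated by the stop rule. Give time observed in each mode, since stopped infants contribute less.
- **Presentation.** Give paired counts with confidence intervals first. As descriptive analyses in infants who received both modes, compare any-episode with an exact McNemar test and seconds with a signed-rank test.
- **Unchanged.** Mean saturation and transcutaneous CO₂ stay as secondary outcomes, and the stop rule stays as it is.
- **To reconcile.** Study Population excludes transcutaneous CO₂ above 80, while the cessation limit is above 70, so an eligible infant could enter already beyond the CO₂ threshold. The two passages must be reconciled before that variable can be interpreted.

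The cost is a few sentences and a short program on signals already acquired, with no new patients or procedures. The full trial must be kept in the recording, and sensor artefact must be screened by a rule fixed beforehand. Power for rare events at n = 24 stays low.
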